## SURGICAL TECHNIQUE AND POSTOPERATORY COURSE

The surgical technique that will be used in this scientific research is the modified Bröstrom-Gould technique.

Originally described by Bröstrom in 1966, it is a technique that provides an anatomical reconstruction of the lateral ligament compartment of the ankle in the component of the PAA and the PC, imbricating them with the joint capsule. In 1980 the intervention was modified by Gould, who added, as part of the repair, the suture of the lower part of the extensor retinaculum. The anatomical access to the lateral ligamentous compartment is obtained by means of a small curved cutaneous incision at the apex of the external malleolus; the technique then provides the suture, by means of detached transosseous points, of the ligamentous compartment and of the retinaculum, as previously mentioned.

In the postoperative period the patient will have a period of immobilization (21-30 days) in a pinstriped bootie or Walker tutor. After the first period of immobilization the patient will start walking with progressive load until complete protected by a non-articulated ankle brace, which will take several times a day to mobilize the ankle. At a distance of about 35-60 days, during a second check as per "standard care", the guardian will be abandoned in favor of comfortable footwear and the patient will be able to start the active FKT of muscular and proprioceptive strengthening.

## CLINICAL SCORE

The clinical scores used for the overall assessment of the patient are (see attachments):

- AOFAs
- SPPB
- FAAM
- SF12.

Respectively, the American Orthopedic Foot and Ankle Score (AOFAs), is a clinical test commonly used in scientific literature (Leigheb et al), which serves to evaluate, in terms of value from 0 to 100, autonomy, pain, stability, ankle alignment and patient's heel.

The Short Physical Performance Battery (SPPB) is a test used to evaluate the functionality of the lower limbs. It consists of 3 different sections:

1. evaluation of the balance in 3 tests:

- maintaining the standing joint position for 10 "
- maintaining the semi-tandem position for 10 "(toe on the side of the heel)
- maintaining the tandem position always for 10 "(big toe behind the heel).

The score varies from a minimum of 0 if the patient fails to maintain the standing joint position for at least 10 "to a maximum of 4 if he is able to complete all three tests.

2. gait evaluation on 4 linear meters the score of the section varies based on the time required for the test from 0 if incapable, to 4 if it succeeds to accomplish the task in less than 4.1 "

3. evaluation of the ability to perform, for 5 consecutive times, the sit to stand from a chair without using the upper limbs that for the test must be crossed in front of the chest the score varies from 0 if unable to 4 if the test is carried out in less than 11.2 ".

The total score of the scale therefore has a range from 0 to 12.

Foot and Ankle Ability Measure (FAAM): translation and validation of the Italian version of the ADL module (FAAM-I / ADL) F. SARTORIO, S. VERCELLI, ELISABETTA BRAVINI \*, SERENA BARGERI \*\*, MICHELA MOROSO \*\*,

G. PLEBANI \*\*\*, G. FERRIERO.) Is a test used to assess patient autonomy in everyday life, by means of targeted and specific questions.

The SF12 test is the short version of the SF-36 (link) questionnaire. Through 12 of the 36 questions of the original questionnaire it allows to investigate the two synthetic indexes, PCS Physical Component Summary for the Physical State and MCS Mental Component Summary for the State of Mental. The strong points of this questionnaire are the brevity and the relative ease of use. In Italy, the questionnaire was used inter alia in 2000 in a ISTAT multiscopo survey on the health status of Italians and a reference database is available with data on a sample of 61.434 representative subjects of the Italian population. Also for this short form the literature is rich in experiences and studies that prove its validity and reliability.

## **Study sample**

All continuous variables will be expressed as mean  $\pm$  standard deviation (SD). The dichotomous or pyrotechnic variables will be expressed as frequency and percentage. To test the effects of the treatment on continuous variables, the ANOVA will be used for repeated two-way measurements (2 groups  $\times$  2 times). Percent Delta scores will be calculated for each participant and each continuous outcome as follows:  $(T1 - T0) * 100 / T0$ . To evaluate the effect of categorical variables on the Delta percentage scores one-way ANOVA will be used if the variables will be normally distributed and homoschedastic, otherwise non-parametric tests will be used: Mann Whitney (2 groups, pre and post operative). To evaluate the effect of continuous or rank variables on the percentage Delta scores, the correlation by Spearman ranks will be used. To assess the distribution of values between dichotomous or categorical variables, the Chi Squared Fisher test will be used (2 pre and post operative groups). For all tests,  $p < 0.05$  will be considered significant. Statistical analysis will be carried out using the statistical package for social sciences (SPSS), software version 15.0 (SPSS Inc., Chicago, USA).

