## 2. OBJECTIVES

The aim is to study the effectiveness of the ankle external ligament reconstruction according to the modified Bröstrom-Gould technique through the study of the postural control with:

- a computerized oscillating platform, Delos device ([www.delos-international.com](http://www.delos-international.com)), in particular in its proprioceptive component;
- using the Modified clinical test Star Excursion Balance Test (mSEBT);
- through evaluation questionnaires (FAAM, AOFAs, SPPB).

To date, in fact, there are scientific works, also produced by our Institute (Giannini et al., 2014), which evaluated patients pre- and post-operatively, but only through clinical score.

Patients will then undergo a preoperative evaluation and a second evaluation at an average time of 4 months from the surgery.

Primary outcome: evaluation of the modified Bröstrom-Goulde technique for ankle external ligament reconstruction.

Secondary outcome: comparison between Delos and mSEBT as stability and proprioception evaluation techniques.

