### 3. STUDY DESIGN

Will be included in the study all the patients who undergo surgery for lateral capsular-ligament instability during 18 months after EC approval (probably end on August 2019), in accordance with the criteria specified below. Each patient will sign an informed consent for participation in the study.

Inclusion and exclusion criteria for patients enrolled in the study

The study population consists in patients with chronic post-traumatic lateral ankle instability who must undergo ankle external ligament reconstruction.

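### The treatment test is a two-group by two-time ANOVA in a study that describes one operated cohort: the second factor is undefined, the treatment term is not named, and pre/post labels sit on independent-sample tests

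*Combined protocol and SAP*

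**What the plan says.** All the statistical rules are in the section headed Study sample.

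- **Treatment effect, continuous outcomes:** "the ANOVA will be used for repeated two-way measurements", followed by a bracket giving two groups and two times. The groups are not described, and no term (group, time or interaction) is singled out.
- **Percent change:** "Percent Delta scores will be calculated for each participant and each continuous outcome", as (T1 − T0) × 100 / T0.
- **Factors affecting percent change:** "To evaluate the effect of categorical variables on the Delta percentage scores one-way ANOVA will be used" if the variables are normal and homoscedastic; "otherwise non-parametric tests will be used: Mann Whitney (2 groups, pre and post operative").
- **Dichotomous or categorical variables:** "the Chi Squared Fisher test will be used (2 pre and post operative groups").

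The design sections describe a single cohort. Section 3 (Study design): "Will be included in the study all the patients who undergo surgery for lateral capsular-ligament instability". Section 2 (Objectives): "Patients will then undergo a preoperative evaluation and a second evaluation at an average time of 4 months from the surgery". The surgical section opens with "The surgical technique that will be used in this scientific research" and names one procedure, the modified Bröstrom-Gould. The visit lists before and after surgery are identical. No control, comparator or allocation appears in the text available for review.

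**The concern.** The primary outcome in Section 2 is the evaluation of the surgical technique, and this ANOVA is the only test assigned to the treatment effect. It names a factor that the described design does not contain. The analyst must therefore decide, possibly with data in hand, whether to drop the factor or supply one, and which term to report as the answer.

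The rest of the section does not settle this. Where it does say what its two groups are, they are the two time points, which repeats the time factor. It also attaches those time points to tests built for independent samples. Percent change is computed within patients, but no test of whether it differs from zero is named. Section 4 includes a 0 to 12 score (SPPB), and the plan itself foresees non-normal data, yet no matched alternative such as signed-rank or McNemar appears.

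**Working it through.** The plan gives no sample size, SD or pre-post correlation, so there is no figure of its own to reproduce. Four checks follow.

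**1. What the two-way model can estimate.** The model has four fixed-effect columns: intercept, group, time, group × time. One cohort measured twice supplies two cell means (T0 and T1).

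- Group constant: the group and interaction columns add nothing; rank 2 of 4.
- Group equated with pre/post: with 0/1 coding, group = time and group × time = time; rank 2 of 4.

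Either way only the intercept and the time effect are estimable.

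**2. What the time effect is.** With dᵢ = T1ᵢ − T0ᵢ, the paired statistic is t = mean(d) / (SD(d)/√n) on n − 1 degrees of freedom. With two times and one group, the repeated-measures time F on 1 and n − 1 degrees of freedom equals t². In simulated data with n = 30, both were 1.4797. The estimable term is therefore a valid paired test of change.

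**3. The label on Mann-Whitney.** The plan's formula combines T0 and T1 into one Delta per patient, so n patients give n values. None belongs to before or after surgery, and a pre/post grouping of Delta cannot be formed. Mann-Whitney on Delta makes sense only between different sets of patients, for example by sex.

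**4. What unpaired pre/post testing would cost (illustration).** Assume equal variance σ² at both times and correlation ρ.

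- Paired variance of the mean change: 2σ²(1 − ρ)/n.
- Variance assumed by an unpaired test: 2σ²/n.
- Standard error ratio, unpaired to paired: 1/√(1 − ρ).
- Actual size of a nominal two-sided 5% unpaired test: 2 × [1 − Φ(1.96/√(1 − ρ))].

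| Assumed ρ | SE ratio | Actual size |
|---|---|---|
| 0.3 | 1/√0.7 = 1.20 | 1.9% |
| 0.5 | 1/√0.5 = 1.41 | 0.6% |
| 0.7 | 1/√0.3 = 1.83 | 0.03% |

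For binary data, simulations (10,000 runs, assumed n = 30, latent correlation 0.7) gave a rejection rate under no change of 0.007 for chi-squared and 0.044 for McNemar. With an assumed latent shift of 0.8 SD, power was 0.70 and 0.88. At zero correlation the two tests roughly agree (power 0.65 and 0.63).

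These figures describe pre and post data tested as independent samples. They do not describe the ANOVA time effect, which keeps the pairing.

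**The case against.** The strongest reply is that little is lost for continuous outcomes. With one cohort and two times, time is the only term that can carry the treatment question; it is valid, and it equals the paired t-test. Delta is also computed patient by patient. On this view the ANOVA sentence is loose wording in a translated text. That largely stands, and it limits the severity. It does not remove the defect: the plan still specifies a factor it never defines and leaves the choice of term to the analyst.

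Second, a second factor may have been intended. The mSEBT section measures the length of both limbs and adopts separate improvement thresholds for the right (6.9%) and left (5%) limb. A limb-by-time layout would be estimable and could bear on the effect of surgery. The documents do not say that limb is the factor, and limb would vary within patients rather than form a group. But a reader who infers that the group and interaction terms certainly have zero degrees of freedom goes too far; what the text supports is that the factor is undefined.

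Third, the chi-squared/Fisher harm has no identified target. No categorical outcome compared before and after is named, and the mSEBT threshold is defined on change, so it gives one value per patient and not a paired table. This stands: the harm is conditional.

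Fourth, treating SPPB as continuous is defensible. This also stands; the gap is only that no paired fallback is stated.

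**Conclusion.** The point holds as a fault of specification and should be fixed. Three things are wrong as written: the treatment ANOVA has an undefined second factor and no named treatment term; the pre/post label on Mann-Whitney for Delta cannot be carried out; and chi-squared/Fisher on pre/post groups treats the same patients as independent. In addition, no paired fallback is given for non-normal or ordinal pre/post data.

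Two stronger inferences are not supported. A reader might conclude that the treatment effect cannot be tested or that the pairing is lost for continuous outcomes; the time effect shows otherwise. A reader might also expect false positives; with positive pre-post correlation the unpaired tests err the other way.

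The size is conditional. Wherever pre and post data were in fact tested as independent, the standard error would be 1.20 to 1.83 times too large and a nominal 5% test would reject 1.9% to 0.03% of the time under no change, for assumed correlations of 0.3 to 0.7. The conclusion rests on the single-cohort description; a group definition outside the text available for review cannot be excluded.

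**What to change.** 1. State that the within-patient change, T1 − T0, is the treatment test for each continuous outcome: paired t-test or, if the differences are clearly non-normal, Wilcoxon signed-rank. Report the change with a 95% confidence interval. Remove the group factor. If a second factor was intended, such as limb (within-patient), define it in advance and state which term tests the treatment.
2. For any categorical variable compared before and after in the same patients, replace chi-squared/Fisher with McNemar (two categories) or a marginal homogeneity test (more than two).
3. Keep one-way ANOVA and Mann-Whitney on percent Delta only for comparisons between different sets of patients, and delete the pre/post label there.

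The cost is an edit to the analysis text. No further patients, visits or data are needed.

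### Predictor analyses rest solely on percent change from baseline, unadjusted for T0, which can cost power and create false category differences on outcomes with a wide baseline spread

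*Combined protocol and SAP*

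**What the plan says.** All the relevant text is in the Study sample section, which serves as the statistical analysis plan.

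- **Score.** "Percent Delta scores will be calculated for each participant and each continuous outcome as follows": (T1 - T0) x 100 / T0.
- **Categorical predictors.** "To evaluate the effect of categorical variables on the Delta percentage scores one-way ANOVA will be used", with Mann-Whitney as the fallback if the assumptions fail.
- **Continuous or rank predictors.** "To evaluate the effect of continuous or rank variables on the percentage Delta scores, the correlation by Spearman ranks will be used".
- **Treatment effect, tested separately.** "To test the effects of the treatment on continuous variables, the ANOVA will be used for repeated two-way measurements". This test does not use the percent score.

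No predictor analysis uses absolute change or includes T0 as a covariate.

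Two of the scales have stated limits. AOFAS is scored "in terms of value from 0 to 100", and for SPPB "The total score of the scale therefore has a range from 0 to 12". The mSEBT section judges improvement by a percentage increase (6.9% for the right limb, 5% for the left). That is the only reason the document offers for a percentage measure. It gives none for AOFAS, FAAM, SPPB, SF12 or Delos.

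**The concern.** T0 appears in both the numerator and the denominator of the score, so the same improvement in points counts for more in a patient who starts low. Two problems can follow.

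- **Power.** Dividing by a variable T0 adds variation unrelated to the predictor and skews the score, so real predictors may be missed.
- **False differences.** If two categories of patients start at different levels but gain the same number of points, their percent changes differ. Baseline level can then pass for a predictor of surgical benefit.

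The study is small and non-randomised with respect to these predictors, so categories may well differ at baseline. What is at stake is the credibility of statements about who benefits from the procedure.

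**Working it through.** **Inputs from the document.** The formula, the tests and the 0.05 threshold come from the Study sample section, and the scale limits from the Clinical score section. T1 comes from "a second evaluation at an average time of 4 months from the surgery". Sample size is not stated; the design section says only "Will be included in the study all the patients who undergo surgery for lateral capsular-ligament instability during 18 months after EC approval". The document gives no baseline mean, SD, T0-T1 correlation or effect size, so there is no planned figure to reproduce. Every numerical input below is an assumption; tests are two-sided.

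**Step 1: how the formula behaves.** A 20-point gain scores 20/40 = 50% from a baseline of 40, 20/60 = 33% from 60, and 20/80 = 25% from 80.

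**Step 2: power with additive gains.** Assume 40 patients in two equal categories, baseline 65 ± 15, correlation r = 0.5, a common gain of 25 points, and an extra 0.8 x 15 = 12 points in one category.

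- T1 - T0: SD of change = 15 x √(2 x (1 - 0.5)) = 15, so the standardised effect is 12/15 = 0.80. Simulated power is 71%.
- T1 adjusted for T0: residual SD = 15 x √(1 - 0.5²) = 13.0, so the standardised effect is 12/13.0 = 0.92. Simulated power is 82%.
- Percent change: simulated power is 40%. With no common gain it is 58%, so much of the loss depends on there being a post-operative gain.

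A separate set of simulations (30 per category, 3,000 runs per setting, r from 0.3 to 0.7) shows how the loss depends on baseline spread:

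| Assumed baseline and gain | Percent change | T1 - T0 | T1 adjusted for T0 |
|---|---|---|---|
| 60 ± 15, gain 25 | 42-44% | 78-79% | 84-92% |
| 60 ± 20, gain 25 | 32-34% | 78-79% | 83-91% |
| 85 ± 8, gain 6 (mSEBT-like) | 73-74% | 78-80% | 84-91% |

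**Step 3: false category differences with additive gains.** Assume 60 patients, SD 15, the same true 25-point gain in both categories, baselines 15 points apart and unbounded scores. Percent change rejects in about 19-34% of trials and T1 - T0 in about 5%. With scores capped at 100 and r from 0.5 to 0.85, the rates are 45-72% and 17-35%. For an mSEBT-like outcome with a 6-point gap, percent change rejects in only 5.0-5.8%. With equal baselines it holds its level (4.6%).

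**Step 4: proportional gains.** If every patient gains the same percentage and scores are unbounded, the ordering against T1 - T0 reverses. For an AOFAS-like outcome at r = 0.7, power is 71% for percent change and 64% for T1 - T0. With baselines 10 points apart, percent change rejects in 5% and T1 - T0 in 28%.

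A ceiling changes this again. On a scale that stops at 100, a patient at 80 can gain at most 20/80 = 25%, and a patient at 40 up to 60/40 = 150%. With a true 38% gain capped at 100 and baselines 15 points apart, percent change rejects in 18-31% and T1 - T0 in about 6% (r from 0.5 to 0.85).

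**Step 5: correlation with T0.** With no change at all and r = 0.5, the Spearman correlation of T0 with the score averages -0.47 for percent change and -0.47 for T1 - T0. With a common 25-point gain (60 ± 15, r = 0.5, no category effect) it is -0.70 and -0.48.

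**The case against.** The strongest case for the plan has four parts.

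- **Proportional gains.** A reader might infer that percent change always loses to T1 - T0. The document does not support that: nothing in it says gains are additive, and Step 4 shows the reversal. This stands, but it is weaker on bounded scales such as AOFAS and SPPB wherever patients approach the ceiling.
- **Correlation with T0.** A reader might take the negative correlation with T0 under no change as evidence for T1 - T0. It is not. It is regression to the mean, shared by any change score and equal for the two measures. It supports only the advice not to test a baseline score against its own change.
- **mSEBT.** The mSEBT section gives a reason for a percentage on that outcome, and at its assumed spread the harm is small. This stands in full.
- **The alternatives are not immune.** T1 - T0 also exceeds 5% when scores are capped. T1 adjusted for T0 rejects in 18-70% of trials in the additive case with baseline gaps, because it asks whether patients with the same T0 end differently, not whether categories change by different amounts. This stands, and the fix has to say so.

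A baseline of zero, which would leave the score undefined, is possible on the stated scales. It is implausible in adults aged 18-40 with severe postural instability excluded, and little weight rests on it.

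**Conclusion.** The point holds as a conditional one. Percent change is the sole response for the predictor analyses, with no adjustment for T0. Given a sizeable baseline spread and roughly additive gains, it can cost about 30 percentage points of power against T1 - T0 (71 - 40 = 31) and about 40 against T1 adjusted for T0 (82 - 40 = 42). It can also raise false category differences from about 5% to about 19-34% when categories start a full SD apart. The actual loss in this trial cannot be computed, because the sample size, SDs, correlations and effect sizes are not in the document.

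A reader might infer that the main result on surgery is compromised. It is not, on this ground: the treatment effect is tested by repeated-measures ANOVA on the continuous variables. Nor are the predictor analyses named as a primary or secondary outcome. This is a worthwhile improvement to the predictor analyses and does not undermine the trial.

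**What to change.** In the Study sample section:

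1. Run the categorical and continuous predictor analyses on T1 - T0, in points of each scale.
2. Report alongside a linear model of T1 on T0 plus the predictor. Read it as the more precise answer only where the predictor is unrelated to T0. Where categories differ at baseline, state that the two models answer different questions.
3. Keep percent change as a descriptive column and for the mSEBT improvement threshold.
4. Do not test a baseline score against the change in the same outcome.

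The cost is analysis wording only, since T0 and T1 are already collected at the scheduled visits. The downside is that results appear in points instead of percent and two estimates are shown for each predictor.

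### The rank and categorical tests treat pre- and post-operative values as two independent groups, but they come from the same patients, and no paired alternative is named

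*Combined protocol and SAP*

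**What the plan says.** Section 2 (Objectives) sets out two assessments of each patient: "Patients will then undergo a preoperative evaluation and a second evaluation at an average time of 4 months from the surgery". The section on surgical technique describes one procedure and no comparator: "The surgical technique that will be used in this scientific research is the modified Bröstrom-Gould technique". The visit schedule lists the same measurements before and after surgery.

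The Study sample paragraph contains the whole analysis plan. It has four relevant steps:

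- Treatment effect on continuous variables: "To test the effects of the treatment on continuous variables, the ANOVA will be used for repeated two-way measurements", described as 2 groups by 2 times.
- Change scores: "Percent Delta scores will be calculated for each participant and each continuous outcome as follows", the formula being (T1 − T0) × 100 / T0.
- Effect of categorical variables on those change scores: one-way ANOVA, or, if its assumptions fail, "non-parametric tests will be used: Mann Whitney (2 groups, pre and post operative".
- Dichotomous or categorical variables: "the Chi Squared Fisher test will be used (2 pre and post operative groups".

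The paragraph names no signed-rank, sign, McNemar or marginal-homogeneity test.

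**The concern.** Mann-Whitney, chi-squared and Fisher all assume that the two groups contain different people. Here the plan fills the groups with the same people at two times.

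The Mann-Whitney sentence is also inconsistent with itself. Its outcome is the percent change, which already combines the two time points into one number per patient and so cannot be divided into a pre-operative and a post-operative group. An analyst has to choose between two readings:

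- **Reading A.** The bracket is a slip, and Mann-Whitney compares percent change between different patients, for example men and women. This is valid.
- **Reading B.** Raw pre- and post-operative scores are compared as if they were independent samples. This is wrong.

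Under reading B the p-values are wrong whenever the within-patient correlation is not zero. With positive correlation they are too large, and a real improvement can be missed. Two competent analysts could therefore report different p-values from the same data while both claiming to follow the plan.

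**Working it through.** **Is there a plan figure to reproduce?** No. The documents give a significance level of 0.05 (sidedness not stated; two-sided assumed here) but no sample size, SD, correlation or effect size. Everything below rests on assumed ranges and applies to reading B only.

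**Step 1: true size of an unpaired test on paired data.** With n pairs, common SD σ and correlation ρ, the variance of the difference in means is 2σ²(1 − ρ)/n, but an unpaired test uses 2σ²/n. In large samples the true two-sided size at nominal 0.05 is

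2 × [1 − Φ(1.96 / √(1 − ρ))].

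- ρ = 0: 1.96/1 = 1.96, size 0.050
- ρ = 0.3: 1.96/0.837 = 2.34, size 0.019
- ρ = 0.5: 1.96/0.707 = 2.77, size 0.0056
- ρ = 0.7: 1.96/0.548 = 3.58, size 0.0004

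A negative ρ makes √(1 − ρ) greater than 1 and pushes the size above 0.05, so the error is conservative only when the correlation is positive.

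**Step 2: Mann-Whitney against Wilcoxon signed-rank.** Simulation with 10,000 replicates, bivariate normal scores with unit SD, n = 30 patients:

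| Correlation | Mann-Whitney size | Signed-rank size | Mann-Whitney power, 0.5 SD | Signed-rank power, 0.5 SD | Loss (points) |
|---|---|---|---|---|---|
| 0 | 4.9% | 4.9% | 45% | 45% | 0 |
| 0.3 | 1.8% | 4.4% | 44% | 58% | 14 |
| 0.5 | 0.7% | 4.6% | 44% | 74% | 30 |
| 0.7 | 0.1% | 5.0% | 43% | 92% | 49 |

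The loss depends on sample size and effect. At correlation 0.5 and a 0.5 SD shift, power is 28% against 55% with n = 20, and 75% against 92% with n = 50. At a 0.8 SD shift, for correlations 0, 0.3, 0.5 and 0.7, the loss is about 0, 6, 7 and 5 points with n = 30, about 0, 11, 19 and 22 points with n = 20, and under 3 points with n = 40. At 1.0 SD with n = 30 it is about 1 point or less.

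**Step 3: Fisher and chi-squared against exact McNemar.** The plan names no pre/post categorical endpoint, so this is an illustration: a binary outcome rising from 50% to 75%, n = 40, built from thresholded bivariate normals.

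| Latent correlation | Fisher | Chi-squared (uncorrected) | Exact McNemar |
|---|---|---|---|
| 0 | 55% | 64% | 54% |
| 0.3 | 56% | 66% | 63% |
| 0.5 | 57% | 67% | 71% |
| 0.7 | 58% | 70% | 81% |

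With no true change (50% both times), at latent correlation 0.3, 0.5 and 0.7, chi-squared rejects in 3.4%, 2.1% and 0.7% of replicates and Fisher in 1.8%, 0.9% and 0.3%. McNemar does not gain power everywhere. The reason to use it is that it is valid for paired data.

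**Step 4: which outcomes could be affected.** The repeated-measures ANOVA keeps the pairing through its time factor, so continuous outcomes analysed that way are untouched. The exposure is any pre/post comparison made with a rank or categorical test. SPPB is a plausible case: "The total score of the scale therefore has a range from 0 to 12", and the patients are 18 to 40 years old with severe postural instability excluded, so scores near the ceiling are likely enough to consider.

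**The case against.** The best defence is that reading A is the intended one. The sentence is about how categorical variables affect percent change, and reading A is the only version that can be run on that variable. The paragraph has visible translation errors, so a slip in the bracket is credible. Treatment effects on continuous variables are assigned to repeated-measures ANOVA, and the non-normality clause is attached only to the percent-change step. On this view a paired rank test is a missing option, and no test has been misapplied.

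This limits the consequences but does not clear the text. The same group definition recurs in the chi-squared/Fisher sentence, where no change score is involved to suggest reading A.

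Two further points are fair. First, the only improvement threshold in the documents, the mSEBT gain of 6.9% (right) or 5% (left), gives one yes/no result per patient. It is not a pre/post pair, and McNemar would not apply to it, so the categorical half of the problem has no named target. Second, normal data are a poor model for SPPB. With an assumed rounded, ceiling-limited score (latent mean 12, SD 1.5, n = 30, shift of 0.5 latent SD), the losses at correlations 0.3, 0.5 and 0.7 are about 7, 15 and 30 points, roughly half to three-fifths of those in the normal-score table. The direction holds; the exact sizes do not carry over to SPPB.

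**Conclusion.** The concern holds. Two independent-sample tests are given groups that consist of the same patients, one of the two rules cannot be carried out on the variable it names, and no paired rank or categorical test is provided.

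How much this matters depends on the reading. Under reading A nothing is lost. Under reading B, with an assumed 30 patients and a 0.5 SD shift, the power loss for Mann-Whitney runs from nil at zero correlation to about 49 points at correlation 0.7, and it nearly disappears at a 1.0 SD shift. If the correlation is positive, as is usual for repeated measures, the error is conservative and does not produce false claims of benefit. The assigned analysis of continuous outcomes is not affected. The wording should be corrected before analysis, but the defect does not undermine the trial.

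**What to change.** Amend the Study sample paragraph as follows:

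1. Remove pre- and post-operative as the group definition for Mann-Whitney and for chi-squared/Fisher.
2. For pre/post comparison of ordinal or clearly non-normal scores, specify the Wilcoxon signed-rank test. List in advance the outcomes it applies to (SPPB is a candidate), and state that for those outcomes it replaces the repeated-measures ANOVA, so that two competing tests of one outcome do not remain.
3. For any categorical variable compared before and after surgery, name the variable and specify McNemar, or a marginal-homogeneity test if it has more than two categories. If there is no such variable, say so.
4. Keep Mann-Whitney (Kruskal-Wallis for more than two levels) on percent change, and chi-squared/Fisher, only for comparisons between different patients, and name the grouping variables, such as sex.
5. While editing, state what the 2 groups in the repeated-measures ANOVA are, since only one technique is described.

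The cost is a wording change in one paragraph. No new data, visits or patients are needed.
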